8.2. Definitions of Analysis Sets

The analysis of data will be based on different subsets according to the purpose of the analysis, i.e., efficacy, safety and pharmacokinetic, respectively.

8.2.1. Efficacy analysis set

Response-evaluable Population: The co-primary endpoint of ORR by RECIST v1.1 will be based on the Response-evaluable Population. This population will include all patients with confirmed HPV-16 or HPV-18 associated disease who have received any dose of both study drugs, have a baseline scan with measurable disease, and have at least one follow-up scan (includes discontinuations due to disease progression or death without follow-up scan) with \geq 16 weeks follow-up.

Secondary efficacy analyses will be based on both the Response-evaluable and the As-treated populations. The As-treated Population will include all patients who receive any IP (defined as at least one dose of either study drug).

Table 6 provides a summary of the efficacy endpoints with their corresponding methods of assessment and populations.

Table 6. A Summary of Efficacy Endpoints with Corresponding Methods of Assessment and Populations

unu i opunutons			
Type of efficacy endpoint	Endpoint	Method	Population(s)
Primary	ORR	RECIST version 1.1	Response-evaluable
Secondary	ORR	RECIST version 1.1	As-treated
	ORR	irRECIST	Response-evaluable and As-treated
	DCR-24w	RECIST version 1.1	Response-evaluable and As-treated
	PFS	RECIST version 1.1	Response-evaluable and As-treated
	OS	Kaplan-Meier	Response-evaluable and As-treated

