1.6. Study Design

This study will be an open label, multi-cohort, phase II trial for the combination therapy of MEDI0457 (INO-3112) and Durvalumab (MEDI4736) in patients with HPV-16 and/or -18 related malignancies. This study will enroll 3 cohorts of patients with HPV-16/18 (+) tumors. The three cohorts are:

- 1. HPV-16/18 cervical cancer,
- 2. HPV-16/18 rare tumors (anal, penile, vulvar, vaginal), and
- 3. HIV (+) HPV-16/18 malignancies (any site).

Each cohort will have a two-stage design with predetermined stopping rules based on ORR after stage I and each cohort will function independently clinically. After each cohort completes accrual to stage I, only the two cohorts with the most responses will move on to stage 2.

Therefore, accrual to stage 2 will not start till all three cohorts have completed stage I. However, if a single cohort has a high response rate (≥4 responses out of 9 patients), the second stage of accrual may proceed prior to other cohorts completing stage I.

At the onset of the study, only patients with cervical, vulvar, or vaginal cancers will be enrolled for the first 3 slots. Once all 3 of these patients have completed the first 6 weeks of treatment, enrollment will be opened to all included cancer histotypes.

Both MEDI0457 and durvalumab treatment will continue until confirmed disease progression or unacceptable toxicity. Either treatment may be stopped by the investigator if a SAE is deemed to be related to that treatment while the other treatment continues.

The target population consists of male or female patients 18 years of age or older with recurrent or metastatic HPV 16- or 18-associated cancers with persistent or progressive disease (PD) after initial standard-of-care treatment and lacking a curative treatment option.

Eligible patients must have at least one "measurable target lesion"—according to RECIST version 1.1—that has not been previously irradiated. In addition, if the primary lesion is not large enough for a biopsy without changing radiologic findings for following response, one additional lesion

Version Number: 1.8 Date: July 26, 2019

Proprietary of MD Anderson Cancer Center

that can be safely biopsied at screening and prior to the first dose of MEDI0457 at Week 1 will be required.

All patients will receive combination treatment with MEDI0457 and durvalumab as per the **Planned Dosing Schedule (Section 4.4.1, Figure 1**, and **Table 3**).

[figure not shown]

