3.4. Discontinuation of Investigational Product

An individual patient will not receive any further IP if any of the following occur.

- Initiation of subsequent anticancer therapy including another investigational agent.
- Confirmed PD: the initial assessment of PD by RECIST v1.1 (baseline PD assessment) will be confirmed by a repeat evaluation at the next tumor assessment time point, but no sooner than 4 weeks later. If any tumor assessment time point (beyond the first PD assessment) shows ≥ 20% increase in the overall tumor burden (the sum of diameters of target lesions and new lesions), when compared to the baseline PD assessment (the sum of diameters of target lesions and new lesions), the patient would be deemed as having confirmed PD and must be discontinued.
- An AE that, in the opinion of the Investigator, supporting company, or the MDACC IND Office, contraindicates further dosing.
- Patient experienced a DLT as defined in Section 6.7.2.
- Withdrawal of consent from further treatment with IP or lost to follow-up.

Version Number: 1.8 Date: July 26, 2019

Proprietary of MD Anderson Cancer Center

- Patient is determined to have met one or more of the exclusion criteria or failed to meet all of the inclusion criteria for study participation and continuing to receive IP might constitute a safety risk.
- Pregnancy or intent to become pregnant.
- Non-compliance with the study protocol that, in the opinion of the Investigator, supporting company, or the MDACC IND Office, warrants withdrawal from treatment with IP (e.g., refusal to adhere to scheduled visits).
- The treating Physician determines it is not in the best interest of the patient to continue.

At any time, patients are free to discontinue IP or withdraw from the study (i.e., IP and assessments) without prejudice to further treatment. If a patient is withdrawn from study, see Section 3.5.2.

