4.4. Doses and Treatments

4.4.1. Planned Dosing Schedule

All patients will receive combination treatment with MEDI0457 and durvalumab as per the following **Planned Dosing Schedule** (treatment should be given at the beginning of the week, unless otherwise specified) as detailed in **Figure 1** and **Table 3**.

Durvalumab will be administered at a fixed dose of 1500 mg q4wk for patients that are \ge 30 kg. For patients who weigh <30 kg, weight-based dosing will be used at a dose of 20 mg/kg q 4 weeks, and if their weight increases to \ge 30 kg they can be switched to durvalumab at 1500 mg every 4 weeks.

Patients will receive 7 mg MEDI0457 delivered by IM followed by EP on Day 1 (Week 1), Week 3, Week 7, Week 12 and then every 8 weeks until disease progression or unacceptable toxicity. Durvalumab will be administered on Week 4, Week 8, Week 12 and then every 4 weeks until disease progression or unacceptable toxicity. On days when both MEDI0457 and durvalumab administrations will occur on the same day (Week 12 then every 8 weeks), MEDI0457 will be administered first, and durvalumab IV infusion will start approximately 1 hour after MEDI0457 is delivered intramuscularly followed by EP.

Minimum time between Week 3 MEDI0457 dose and the Week 4 first durvalumab dose, and the Week 7 MEDI0457 dose and the Week 8 durvalumab dose is 7 days.

Version Number: 1.8 Proprietary of MD Anderson Cancer Center Page 1019 26 2019

4.4.2. **Durvalumab**

Durvalumab will be administered at a fixed dose of 1500 mg q4w in the combination and monotherapy arms for patients weighing \geq 30 kg. For patients weighing \leq 30 kg, the dose will be 20 mg/kg. The maximum number of doses of checkpoint inhibitor therapy will equal 13.

The duration will be approximately 1 hour (± 5 minutes) for each durvalumab infusion. A 1- hour observation period is required after the first infusion of durvalumab is administered. If no clinically significant infusion reactions are observed during or after the first dose, subsequent infusion observation periods can be at the investigator's discretion (suggested 30 minutes after each durvalumab infusion).

Patients will be monitored during and after the infusion with assessment of vital signs at the times specified in the study protocol.

See Section 6.7.1 dose administration changes in the event of Grade 1 or 2 infusion-related reactions.

4.4.3. **MEDI0457**

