Of note, clinically significant deterioration is considered to be a rapid tumor progression that necessitates treatment with anti-cancer therapy other than the study regimen or other symptomatic progression that requires urgent medical intervention (e.g., central nervous system metastasis, respiratory failure due to increasing malignant pleural effusion, or development of mechanical bowel obstruction due to carcinomatosis or tumor compression)

6.4. **HPV-16 or HPV-18 Testing**

Patients will be enrolled into the study based on a fresh or historical sample that has been tested and is positive for HPV-16 or HPV-18 positive by the institutionally approved assay. Please refer to section 6.6.1 for details regarding tissue collection.

6.5. **Safety Assessments**

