6.7. Management of IP-related Toxicities

6.7.1. **Dose Management**

Either treatment may be stopped by the investigator while the other treatment continues. MEDI0457 doses should not be modified.

For AEs that are considered at least partly due to administration of durvalumab the following dose adjustment guidance may be applied:

- Treat each of the toxicities with maximum supportive care (including holding durvalumab).
- If the symptoms promptly resolve with supportive care, consideration should be given to continuing the same dose of durvalumab along with appropriate continuing supportive care. If medically appropriate, dose modifications are permitted for durvalumab.
- All dose modifications should be documented with clear medical reasoning and documentation of the approach taken.

In addition, there are certain circumstances in which durvalumab should be permanently discontinued (Appendix D, Postow 2015).

Following the first dose of durvalumab, subsequent administration of durvalumab can be modified based on toxicities observed (Appendix D, Postow 2015). All toxicities will be graded according to NCI CTCAE version 4.03.

Based on the mechanism of action of durvalumab leading to T-cell activation and proliferation, there is the possibility of observing irAEs during the conduct of this study. Potential irAEs include immune-mediated dermatitis, hepatitis/hepatotoxicity, endocrinopathy (hypothyroidism, hyperthyroidism, hypophysitis, and adrenal insufficiency), neuropathy/neuromuscular toxicity, nephritis, pancreatitis (elevated lipase/amylase), pneumonitis, and colitis. Patients should be monitored for signs and symptoms of irAEs. In the absence of an alternate etiology (e.g., infection or PD) signs or symptoms of dermatitis, hepatitis/hepatotoxicity, endocrinopathy

Version Number: 1.8

Proprietary of MD Anderson Cancer Center Date: July 26, 2019

(hypothyroidism, hyperthyroidism, hypophysitis, and adrenal insufficiency), neuropathy/neuromuscular toxicity, nephritis, pancreatitis (elevated lipase/amylase), pneumonitis, and colitis should be considered to be immune-related.

Dose modifications will not be required for AEs that are clearly not attributable to durvalumab (such as an accident) or for laboratory abnormalities that are not deemed to be clinically significant. Administration may continue despite concurrent vitiligo of any AE grade.

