Grade 2	For Grade 2: If persistent injection site reaction lasting more than 10 days despite optimal management, MEDI0457 next dose of vaccine should be omitted. Durvalumab to continue dependent on discussion of investigator with medial monitor. For second occurrence of Grade 2: In the setting of second occurrence of persistent ≥ Grade 2 injection site reaction for more than 7 days despite optimal medical management, permanently discontinue MEDI0457 and durvalumab.	 Symptomatic treatment with over-the-counter analgesics (opioids should be avoided unless necessary) and supportive care (i.e. cold compress) If pain persists for 3 days, contact investigator
Grade 3 or Grade 4	For Grade 3: Injection should be held until the toxicity resolves to Grade 1 or baseline. • If resolution occurs within 5 days, consider continued dosing of MEDI0457 and durvalumab at the current schedule as long as the adverse event of concern was not considered life threatening. • If the Grade 3 injection site toxicity only improves to Grade 2 within 5 days then omit next dose of MEDI0147 and continue durvalumab dependent on discussion of investigator with medical monitor. • If no change of Grade 3 reaction within 5 days, then permanently discontinue MEDI0457 and durvalumab. For Grade 4: Permanently discontinue MEDI0457 and durvalumab.	 For Grade 3 or Grade 4: Consult investigator for evaluation (rule out infection or other causes) and treatment (opioids may be considered) Obtain dermatology/surgical consult Consider hospitalization

Version Number: 1.8 Date: July 26, 2019

Proprietary of MD Anderson Cancer Center

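### The primary ORR set requires a dose of both drugs, so patients who die or progress clinically before the first durvalumab dose at Week 4 drop out of it

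*Combined protocol and SAP*

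**What the plan says.** Section 8.2.1 bases the primary ORR on the Response-evaluable Population. Besides confirmed HPV-16/18 disease, its members must have "received any dose of both study drugs, have a baseline scan with measurable disease, and have at least one follow-up scan", with at least 16 weeks of follow-up. A parenthesis directly after the scan condition reads "includes discontinuations due to disease progression or death without follow-up scan".

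Section 4.4.1 staggers the two drugs. MEDI0457 is given on Day 1 and at Week 3, and "Durvalumab will be administered on Week 4, Week 8, Week 12 and then every 4 weeks". Table 3 shows the same order.

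Table 6 makes ORR in the As-treated Population (any dose of either drug) a secondary analysis. Section 8.1.1 states the decision rule for each cohort in evaluable subjects: stop at 1 or fewer responses in 9, and succeed at 9 or more in 34. It does not define evaluable. Section 8.1.2 sets the null ORR at 0.15 and the alternative at 0.35, without saying whether they describe all treated patients or recipients of both drugs.

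**The concern.** Receiving durvalumab is an event after baseline, and it depends on surviving and staying well enough for about three weeks. A set that requires it leaves out the earliest failures. The parenthesis shows that the plan wants early failures counted, but as placed it excuses the absent scan and not the absent second drug. A death without a scan is therefore a non-response at Week 5 and disappears from the primary analysis at Week 3, only because of the dosing order.

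The documents contain a concrete route. Section 6.3 describes clinically significant deterioration as including "rapid tumor progression that necessitates treatment with anti-cancer therapy other than the study regimen", and Section 3.4 ends study treatment on "Initiation of subsequent anticancer therapy including another investigational agent". A patient who follows that route before Week 4 has had MEDI0457 only.

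At stake is the meaning of the primary ORR and, under conditions given in the working, the error rate of the go/no-go rule.

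**Working it through.** **1. Is the patient outside the set?** Take a patient dosed on Day 1 who dies in Week 3.
- Any dose of both drugs: not met, because durvalumab starts at Week 4.
- Follow-up scan: excused by the parenthesis.
- Result: outside the primary set, inside As-treated.

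Move the death to Week 5, after one durvalumab dose. The both-drugs condition is met, the scan is excused, and the patient is a non-response. (This takes the 16-week condition as not cancelling the exception; otherwise the exception would do little for early deaths.)

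**2. The plan's own design.** With b(x; 9, p) the binomial probability of x responses in 9 and Y ~ Bin(25, p),

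P(go | p) = Σ (x = 2 to 9) b(x; 9, p) × P(Y ≥ 9 − x).

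- p = 0.15: 0.0474 (limit 0.05).
- p = 0.35: 0.8107 (target 0.80).
- A search for the Simon optimal design returns the stated 1/9 and 8/34 cut-offs, and 9 + 2 × 34 = 77.

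The design is reproduced. It is a per-cohort calculation, as in 8.1.2, and ignores the rule that only two cohorts advance.

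**3. Effect on the estimate.** Let e be the share of treated patients left out, all non-responders. The documents give no value, so e = 1%, 3% and 5% are assumptions. If the treated-patient ORR is 0.15, the primary set shows 0.15/(1 − e):
- e = 1%: 0.15/0.99 = 15.2%
- e = 3%: 0.15/0.97 = 15.5%
- e = 5%: 0.15/0.95 = 15.8%

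The direction is fixed, since removing patients who add nothing to the numerator cannot lower the ratio. In counts, one such patient left out turns 9 of 35 treated (25.7%) into 9 of 34 (26.5%).

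**4. Effect on the decision rule.** If evaluable in 8.1.1 means this set and the 15% null refers to treated patients, put 0.15/(1 − e) into the formula:

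| e | P(go) |
|---|---|
| 0 | 0.0474 |
| 1% | 0.0501 |
| 3% | 0.0558 |
| 5% | 0.0622 |

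If the null refers to recipients of both drugs, the rule applied to this set keeps 0.0474. If evaluable means treated patients and the null does too, it is also 0.0474. The table further assumes that the both-drugs restriction applies at stage 1 with the 16-week condition set aside, because that look is triggered at 8 weeks.

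**5. Cost of including these patients.** If 35% is the ORR among recipients of both drugs, the wider set has 0.35(1 − e):
- e = 1%: 0.3465, power 0.8015
- e = 3%: 0.3395, power 0.7819
- e = 5%: 0.3325, power 0.7608

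If 35% refers to treated patients, power stays 0.8107.

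**The case against.** **The As-treated ORR already contains these patients.** True, and readers will see both figures. But it is secondary, and nothing ties it to the 2/9 and 9/34 rules.

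**ORR among recipients of both drugs is a legitimate target.** The objective in 2.1 and the success statement in 8.1.1 both concern the combination, and 8.2.1 names both drugs. This stands as a possible choice. The plan does not state it as its target, and the exception in the same sentence points towards counting early failures.

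**The parenthesis could be read as widening the whole population.** That is possible. Its position and its own mention of the scan make the narrower reading more natural, and one sentence would settle it.

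**The route is narrow.** This stands. The gap is about three weeks, patients are ECOG 0 or 1 (3.1), and no scan is scheduled before Week 4, so losses come from death or clinical progression. A patient who worsens but receives one durvalumab dose stays in. In HPV-005, a different population, all 20 patients received four MEDI0457 doses (1.2.1).

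A reader might also infer that early toxicity stops bias the ORR upwards in the same way. The documents do not support that. Section 1.6 says "Either treatment may be stopped by the investigator if a SAE is deemed to be related to that treatment while the other treatment continues", and 6.7.1 says "Either treatment may be stopped by the investigator while the other treatment continues", so stopping MEDI0457 need not prevent durvalumab. Appendix E does have reactions that stop both ("If no change of Grade 3 reaction within 5 days, then permanently discontinue MEDI0457 and durvalumab"), but such a patient could still be scanned and respond, so the direction is uncertain.

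**Conclusion.** The point holds for deaths and clinical progression before the first durvalumab dose. They leave the primary ORR while the same events after that dose count as non-responses, and this can only raise the primary ORR relative to treated patients. The shift is 0.2, 0.5 or 0.8 percentage points on a true 15% at assumed losses of 1%, 3% or 5%. The true size is unknown and probably small.

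A reader might infer that the trial's 5% error rate is exceeded. That does not follow from the documents. It needs both conditions in step 4 of the working, and the plan states neither. Nor do the documents support the inference that the sample size is wrong: the stated design reproduces exactly. The mismatch between the 8-week stage 1 trigger and the 16-week follow-up condition is a separate point and adds no weight here.

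**What to change.** **8.2.1.** Extend the existing exception. Patients with confirmed HPV-16/18 disease and measurable disease at baseline who received any study drug, and who died or stopped for disease progression before the first durvalumab dose, stay in the primary set as non-responders. Say that progression here includes clinically significant deterioration as described in 6.3, and that the scan and 16-week conditions do not apply to these patients.

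**8.1.1.** Say that these patients count among the 9 and the 34.

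**8.1.2.** State the power consequence below.

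Leave the handling of toxicity stops, the assessment rule in 8.3.1, the sample size and Table 6 as they are.

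**Cost.** A few sentences, with no new data or visits. The primary ORR becomes slightly lower. If 35% refers to recipients of both drugs, power is about 0.80, 0.78 or 0.76 at 1%, 3% or 5% early failure, in place of 0.81. Stating and accepting that small loss is enough.

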8.2.2. Safety analysis set

The safety evaluation will be based on the As-treated Population and the Safety analysis set will include all patients who receive any IP (defined as at least one dose of either study drug).

8.2.3. Pharmacokinetics analysis set

The pharmacokinetic analysis set will include all patients who receive at least one dose of durvalumab and have any post-dose data available and have at least one post dose plasma concentration measurement at a scheduled time point without any important protocol deviations or violations thought to significantly affect the pharmacokinetic of the drug.

Version Number: 1.8 Date: July 26, 2019

Proprietary of MD Anderson Cancer Center

8.3. Outcome Measures

8.3.1. Primary

The primary objective will be measured by ORR by RECIST v1.1. The ORR will be estimated along with corresponding 95% confidence interval. All analysis will be done within each cohort as well as across all cohorts.

All RECIST assessments, whether scheduled or unscheduled, will be included in the calculations. This is also regardless of whether a patient discontinues study treatment or receives another anticancer therapy.

At each visit, patients will be assigned a RECIST version 1.1 visit response of CR, PR, SD, or PD depending on the status of their disease compared with baseline and previous assessments by the investigator. Baseline will be assessed within the 28 days prior to enrollment. If a patient has had a tumor assessment that cannot be evaluated, then the patient will be assigned a visit response of not evaluable (unless there is evidence of progression in which case the response will be assigned as PD).

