5. STUDY PLAN

All study procedures will be performed according to **Table 3**.

Version Number: 1.8 Date: July 26, 2019

Proprietary of MD Anderson Cancer Center

Table 3. Schedule of Study Procedures

	Screening	(Cycle 1		Cyc	ele 2	Cy	cle 3	Cycle 4 ^a	Cycle 5 ^a	EOT ^b	Follow-up ^c
Week of Study	-	1	3	4	7	8	10	12	16	20	-	-
Procedures Day of Week	-28 to -1	1 ±7 days (unless otherwise noted)										
Informed consent	X											
Demographics	X											
Medical histories ^d	X											
Inclusion/exclusion criteria	X	X										
Physical examination ^e	X	Xf	X	X	X	X	X	X	X	X	X	
ECOG performance status	X	X^{f}	X	X	X	X	X	X	X	X	X	
Adverse events assessment	X	X	X	X	X	X	X	X	X	X	X	
Concomitant medications/procedures	X	X	X	X	X	X	X	X	X	X	X	
Disease status ^g	X ^h							Xi		X ^{i,j}	X	X^k
Hepatitis/HIV screening ¹	X											
Vital signs ^m	Xg	Xf	X	X	X	X	X	X	X	X	X	
12-lead ECG	X	Xf				X		X		X ⁿ	X	
HPV typing ^o	X											
Hematology ^p	X	Xf	X	X	X	X	X	X	X	X^q	X	
Serum chemistry ^r	X	Xf	X	X	X	X	X	X	X	X^q	X	
Coagulation testing ^s	X	As clinically indicated.										
Thyroid function testing ^t	X	X^{f}		X		X		X	X	X^q	X	
Urinalysis ^u	X	As clinically indicated.										
Pregnancy test ^v	X^{w}	X ^x		X		X		X	X	X	X	
MEDI0457 administration ^y		X	X		X			X		X		
MEDI0457 post-treatment reaction ^z		X	X		X			X		X		
Download EP data		X	X		X			X		X		
Durvalumab administration ^{aa}				X		X		X	X	X		
Tumor biopsy ^{bb}	X						Xcc				X^{dd}	
Immune Profiling/HPV Serology Research Bloodee		X		X		X	X		$X^{\rm ff}$		X	
Pharmacokinetics/ADA Research Blood ^{gg}				X		X			X^{hh}			
Viral load ⁱⁱ	X			X		X		X	X	X	X	
HBV DNA/Hep BsAg ^{jj}				X		X		X			X	

Version Number: 1.8

Proprietary of MD Anderson Cancer Center Date: July 26, 2019

- ^a Patients can continue on the study until progression or unacceptable toxicity as long as the physician feels the patient is receiving benefit. Cycles 4 and 5 should be repeated to continue this treatment. ^b End of treatment (EOT) is defined as the last visit where the decision is made to discontinue protocol directed treatment.
- ^c A clinic visit is not required for follow-up. Patients who are taken off study due to disease progression or intolerable toxicities will be followed for vital status every 6 months via phone and/or review of medical record.
- ^d Histories include medical history, history of prior cancer treatment, history of procedures

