Patients who discontinued from treatment for reasons other than PD will continue disease assessments until confirmed PD or start of subsequent anticancer therapy.

The response to immunotherapy may differ from the typical responses observed with cytotoxic chemotherapy including the following:

- Response to immunotherapy may be delayed,
- Response to immunotherapy may occur after PD by conventional criteria,
- The appearance of new lesions may not represent PD with immunotherapy, and/or
- SD while on immunotherapy may be durable and represent clinical benefit.

Based on the above-described unique response to immunotherapy and based on guidelines from regulatory agencies, e.g., European Medicines Agency's "Guideline on the evaluation of anticancer medicinal products in man" (EMA/CHMP/205/95/Rev.4) for immune modulating anticancer compounds, this study will include the following in addition to standard RECIST 1.1 criteria:

- RECIST will be modified so that PD must be confirmed with a second radiologic assessment, preferably, 5 weeks (+/- 7 days) after the initial assessment of PD in the absence of clinically significant deterioration. Treatment with study regimen should continue between the initial assessment of progression and confirmation for progression at outlined in Tables 4.
- In addition, subjects may continue to receive the study regimen beyond confirmed PD in the absence of clinically significant deterioration and if investigators consider that subjects may be deriving benefit from treatment and there are no more suitable alternative treatments available for the subject.

Version Number: 1.8

Proprietary of MD Anderson Cancer Center Date: July 26, 2019

Modification of RECIST as described is meant to discourage the early discontinuation of the study regimen and provide a more complete evaluation of its anti-tumor activity than would be seen with conventional response criteria. Nonetheless, the efficacy analysis will be conducted by programmatically deriving each efficacy endpoint based on the first evidence of progression (by modified RECIST 1.1 criteria described below) when progression is confirmed by a second scan.

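### The primary ORR takes in scans made after another anticancer therapy, and nothing bars counting a response first seen after a switch without confirmed progression

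*Combined protocol and SAP*

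**What the plan says.** **Counting rule.** Section 8.3.1 defines the primary endpoint as ORR by RECIST 1.1 and states: "All RECIST assessments, whether scheduled or unscheduled, will be included in the calculations". The next sentence reads: "This is also regardless of whether a patient discontinues study treatment or receives another anticancer therapy".

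**Collection rules that stop at new therapy.** Section 6.3 says: "Patients who discontinued from treatment for reasons other than PD will continue disease assessments until confirmed PD or start of subsequent anticancer therapy". Section 6.3 repeats this for toxicity discontinuations, and Table 3 note g says the same. Under Table 3 note c, patients taken off study for progression or intolerable toxicity "will be followed for vital status every 6 months via phone and/or review of medical record".

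**Collection rules with no such stop.** Table 3 note k, and parallel text in Section 6.3, schedule scans for patients without progression from Day 90 after end of treatment through to end of study. Neither mentions new therapy.

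**Progression rule.** Section 6.3 derives each efficacy endpoint "based on the first evidence of progression (by modified RECIST 1.1 criteria described below) when progression is confirmed by a second scan". It also says that "PD must be confirmed with a second radiologic assessment, preferably, 5 weeks (+/- 7 days) after the initial assessment of PD", but limits this to patients without clinically significant deterioration. One form of that deterioration is "rapid tumor progression that necessitates treatment with anti-cancer therapy other than the study regimen".

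**Switching is foreseen.** Section 3.4 lists as a separate reason to stop study drug: "Initiation of subsequent anticancer therapy including another investigational agent".

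**The concern.** There is no control arm. Section 8.1.1 calls the combination worthy of further study at 9 or more responses of 34, against a null ORR of 15% (Section 8.1.2). If a patient who has not responded starts another drug and then shows a CR or PR, Section 8.3.1 as written includes that scan, and the response is attributed to MEDI0457 plus durvalumab. One such patient can turn 8/34 (23.5%) into 9/34 (26.5%).

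The progression rule in Section 6.3 does not close the gap. A patient who switches with no progression has no progression date to anchor on. For a patient with one progressive scan, clinical deterioration and an immediate switch, two analysts could read Sections 6.3 and 8.3.1 differently.

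**Working it through.** **1. Which patients are exposed**

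| Patient | Section 6.3 progression rule | Section 8.3.1 |
|---|---|---|
| Progression confirmed by a second scan, then a switch | Can be read as barring later responses | Scan included, but 6.3 can govern |
| One progressive scan with clinically significant deterioration, switch, no second scan | Ambiguous: confirmation is asked for only without deterioration, yet the derivation sentence requires a second scan | Scan included |
| Switch with no progression | Does not apply | Scan included; no cut-off anywhere |

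The gap is the third row, and the second row on one of its two readings.

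**2. Can such scans exist?** Note g and the Section 6.3 sentences end scanning at subsequent therapy. Note k and its parallel text continue scanning if there is no progression. Either g limits k, and post-switch scans are off schedule, or k stands, and some are on schedule. Section 8.3.1 accepts both kinds.

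**3. The plan's own figures.** Inputs from Sections 8.1.1 and 8.1.2: 9 patients in stage 1, continue with 2 or more responses, 34 in total, success at 9 or more, null 0.15, alternative 0.35.

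P(success | p) = Σ over x = 2 to 9 of b(x; 9, p) × P[Bin(25, p) ≥ 9 − x]

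- p = 0.15: 0.0474 (stated level 0.05)
- p = 0.35: 0.8107 (stated power 80%)

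The stated design reproduces.

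**4. Illustration of size.** The documents give no rate for these scans. Assume that a share q of patients has a post-switch scan and that a fraction s of the non-responders among them respond. Only non-responders can become new responders, so at the null:

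apparent p = 0.15 + 0.85 × q × s; extra responses per 34 = 34 × 0.85 × q × s

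The range for q is 2%-5%. The range for s is 10%-25%; Section 1.3.1 says current options rarely exceed 25%.

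| q | s | Extra per 34 | Apparent null ORR | Type I error, counted at both looks | Type I error, counted only at the final look |
|---|---|---|---|---|---|
| 0 | – | 0 | 15.0% | 4.7% | 4.7% |
| 2% | 10% | 34 × 0.85 × 0.002 = 0.06 | 15.2% | 5.0% | 5.0% |
| 5% | 15% | 34 × 0.85 × 0.0075 = 0.22 | 15.6% | 5.9% | 5.7% |
| 5% | 25% | 34 × 0.85 × 0.0125 = 0.36 | 16.1% | 6.8% | 6.4% |

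The last column keeps the stage 1 rate at 15%, because Section 8.1.3 calls for the stage 1 report once nine patients have completed 8 weeks of treatment. Later responses then enter only the final count.

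As a bounding case, one such response always added at the final look lowers the effective boundary to 8/34 and gives 0.095.

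**5. Denominator.** Section 8.2.1 requires a follow-up scan but already admits patients who stop for progression or death without one. Only a patient who switches for another reason with no earlier follow-up scan depends on a post-switch scan to be in the set.

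**The case against.** The strongest reply is that the protocol's own stop rules make these scans rare. If note g governs and is followed exactly, no post-switch scan exists and type I error stays at 4.7%. This stands as a limit on size. It does not settle what to do with a scan that does exist: these are rules about collecting scans, note k has no such stop, and Section 8.3.1 expressly takes unscheduled scans.

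A second reply is that progression with clinical deterioration may need no second scan, so Section 6.3 would already bar later responses in rapid progressors. That reading is fair, and on it the gap shrinks to patients who switch without radiologic progression. The derivation sentence points the other way, so the text remains ambiguous.

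A third reply is that Section 8.3.1 is a deliberate, prespecified choice to ignore switching. For a patient who switches with no progression the sentence is indeed explicit. But Section 1.5 frames the hypothesis as anti-tumor activity of this combination, and no rationale is given for crediting it with responses to later drugs.

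A reader might infer three stronger points that the documents do not support:

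- **Responses after confirmed progression are counted.** Section 6.3 can be read as excluding them.
- **The false-positive rate is known to be inflated.** There is no rate to base that on, and the low end of the illustration is about the nominal 5%.
- **The denominator is broadly distorted.** Section 8.2.1 already admits progressors without a follow-up scan.

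**Conclusion.** The point holds in limited form. Section 8.3.1 includes post-switch scans in the primary ORR, and no section bars counting a CR or PR first seen after a switch without confirmed progression. The collection rules conflict, so they cannot be relied on to prevent it.

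The frequency is not given and is probably low. At the assumed 2%-5% of patients scanned after a switch and 10%-25% response among their non-responders, 0.06-0.36 extra responses per 34 are expected. Type I error per cohort is then about 5.0%-6.8%, against 4.7% without them. These figures illustrate scale and are not estimates. The defect is in the definition of the primary endpoint. It should be fixed because a single patient can decide the result and the correction is cheap.

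**What to change.** In Section 8.3.1, keep the statement that assessments after discontinuation of study treatment are included, since responses to immunotherapy may be delayed. Delete the closing clause on receipt of another anticancer therapy, and add:

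> Only CR or PR documented before RECIST 1.1 progression (as determined under Section 6.3) and before the start of any subsequent anticancer therapy counts toward ORR; later scans are listed but not counted as responses, and patients without an earlier response remain in the denominator as non-responders.

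Then:

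- Align the Response-evaluable definition in Section 8.2.1, so that a patient who switches for a reason other than progression with no earlier follow-up scan is explicitly kept in.
- Apply the same rule to the As-treated ORR.
- State, for analysis only, whether the palliative local treatment of non-target lesions permitted in Section 3.3.1 counts as subsequent therapy.
- Reconcile Table 3 notes g and k with Sections 6.3 and 8.3.1, and say in 6.3 how progression with clinical deterioration and no second scan is dated.
- If wanted, keep the all-scans ORR as a sensitivity analysis.

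**Cost.** Text changes only, using the start date of subsequent therapy, on which Sections 3.4 and 6.3 already depend. The sample size is unchanged. The reported ORR may be slightly lower: at the null and the assumed rates, by 0.85 × 0.002 to 0.85 × 0.0125, or about 0.2 to 1.1 percentage points. Power stays at 81% if the 35% target means response before subsequent therapy; the documents do not say.
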